3.3 Secondary Study Endpoints

1. Pain intensity (NRS) assessments prior to post-anesthesia care unit (PACU) discharge, every 4 hours beginning on arrival to patient room (to the closet time interval), and prior to hospital discharge or 12 pm on POD 1 (whichever comes first).
2. Opioid consumption in daily oral morphine equivalents (OME) – preoperative, intraoperative, PACU stay, and total beginning on arrival to patient room until patient discharge or up to POD 3 (whichever comes first).
3. Moderate to severe complications during regional anesthesia block placement (inadvertent intravascular injection⁺, inadvertent epidural or subarachnoid injection, local anesthetic systemic toxicity*, and pneumothorax) or during local infiltration analgesia injection (local anesthetic systemic toxicity).
 - a) ⁺*Inadvertent intravascular injection is suspected if a patient experiences sudden loss of consciousness, apnea, convulsions, hypotension, respiratory depression, nausea or dizziness, or stroke symptomology.*
 - b) ^{*}*Local anesthetic systemic toxicity is suspected if a patient has acute onset of central nervous system changes (tinnitus, metallic taste in mouth, perioral numbness) or cardiovascular changes (bradycardia, hypotension, EKG changes).*

4. Peripheral nerve block catheter-related complications including presence of site infection (tenderness to palpation, erythema, swelling, drainage of pus), hematoma, inadvertent catheter dislodgement, and local anesthetic systemic toxicity.
5. Duration of hospital stay (number of days), in addition to reason for hospital length of stay > 1 night (i.e., social work/disposition, inadequate pain control, nausea/vomiting, other)
6. Postoperative follow-up
 - a. Telephone encounter or office visit follow up 12 to 16 weeks postoperatively- NRS pain scores at rest and with movement of surgical extremity, postoperative neurologic changes (persistent numbness, paresthesia, or weakness of surgical extremity), and complications or adverse events will be noted.
7. Questionnaire Forms
 - a) SF-12
 - i. Collected preoperatively and at the 12-16 week postoperative visit or telephone call.
 - b) ASES
 - i. Collected preoperatively and 1-1.5 year postoperative visit or telephone call (data to be used in a follow-up study).
 - c) LANSS
 - i. Collected at 12-16 week follow-up visit to assess neuropathic pain in patients complaining of pain.

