6.1 Pre-Operative Plan

Following informed consent and randomization, study staff will record baseline patient demographics (including baseline NRS values for pain at rest, age, weight, gender, ASA physical status) from the electronic medical record and/or during the patient interview.

NRS pain scores at rest will be measured at the following time points: arrival to post-anesthesia care unit (PACU), prior to PACU discharge, every 4 hours beginning on arrival to patient room. Pain scores will be measured until hospital discharge from the time of the initial assessment in

the recovery room (PACU). All NRS pain scores will be recorded by registered nurses per standard protocol.

Regional Block – Both CISB and SISB:

Based on our current total joint regional anesthesia pathway (MC1156-462rev0115 and MC1156-1321rev1015), all patients will be provided (unless contraindicated and at the discretion of the attending anesthesiologist) a combination of oral analgesic medications preoperatively:

- 1) Tylenol 1 gram – at least 6 hours since last dose
- 2) Celecoxib 400 mg – for patients 18-64 years old and CrCl > 50 mL/min (if lab is available)
- 3)
 - a. Oxycodone (immediate release)
 - i. 5-10 mg once for patients 18-64 years old
- 4) Scopolamine Transdermal patch: 1.5mg - Apply to skin behind ear for 24 hours for high-risk patients (history of motion sickness or postoperative nausea vomiting). This is at the discretion of the anesthesiologist.

Local Infiltration Analgesia (LIA):

- 1) Tylenol 1 gram – at least 6 hours since last dose
- 2) Celecoxib 400 mg – for patients 18-64 years old and CrCl > 50 mL/min (if lab is available)
- 3)
 - a. Oxycodone (immediate release)
 - i. 5-10 mg once for patients 18-64 years old
- 4) Scopolamine Transdermal patch: 1.5mg - Apply to skin behind ear for 24 hours for high-risk patients (Hx: motion sickness or postoperative nausea vomiting). This is at the discretion of the anesthesiologist.

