If patients are randomized to the LIA group, periarticular injection will occur after implantation of the final prostheses, but prior to closure of the fascia. All surgeons will complete the infiltration following a similar protocol, equally distributing the study medication around the glenoid and humerus, subscapularis, deltoid, posterior capsule and subcutaneous tissue.

Regional Block – Both CISB and SISB:

Preoperatively, patients will be sedated, under the discretion of the anesthesiologist, with intravenous midazolam (1-4 mg) and fentanyl (50-200 mcg) for alleviation of anxiety and pain.

Patients randomized to either the CISB or SISB group will follow institutional practice in accordance to the total joint regional anesthesia pathway (MC1156-462rev0115). The interscalene nerve block will be performed under continuous live ultrasound guidance, obtaining visualization of the roots (C5-C6 is ideal) or trunks (Superior Trunk is ideal) of the brachial plexus in between the anterior and middle scalene muscles as described by Chan.⁴¹ An in plane or out of plane approach to needle advancement under live ultrasound guidance will be at the discretion of the anesthesiologist. In cases with poor ultrasound imaging, a combined nerve stimulator and ultrasound guidance technique is acceptable. Appropriate needle placement will be verified by injecting normal saline 0.9% and visualizing spread within the interscalene groove at the level of the roots/trunks of the brachial plexus. Local anesthetic may also be used for hydrodissection in order to navigate needle placement into the correct position. The proceduralist should attempt to use less than 10 mL (if possible) of saline 0.9% to identify correct placement of peripheral nerve block.

Regional Block – SISB

Once needle position is verified, the initial loading dose of local anesthetic solution to be administered is presented in Table 2.

Regional Block – CISB

Once needle position is verified by ultrasound imaging, a continuous catheter device will be placed within the interscalene groove at the level of the roots/trunks of the brachial plexus. After delivery of the catheter, verification of the catheter within the interscalene groove will be assessed by again evaluating spread of normal saline 0.9% or local anesthetic within the interscalene groove.

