7.2 Statistical Methods

Descriptive Statistics

Baseline characteristics will be summarized using mean and standard deviation for continuous variables that have a normal Gaussian distribution, and median and interquartile range for continuous variables with a non-normal distribution. Frequencies and percentages will be used to summarize categorical baseline characteristics. Baseline characteristics will be compared across groups using analysis of variance, or the Kruskal-Wallis test for continuous variables and the chi square test for categorical variables.

The primary aim of this study is to assess whether continuous interscalene nerve block provides superior analgesic benefit via OBAS compared to single injection interscalene blockade and local infiltration analgesia on POD 1 for primary total shoulder arthroplasty. In order to test this hypothesis, the will be compared across groups using ANOVA (or the Kruskal-Wallis test). Supplemental pairwise comparisons will be performed using two-tailed tests with $\alpha=0.017$ (Bonferroni adjusted) used to denote statistical significance. Similar analyses will be performed for secondary endpoints of pain and total additional opioid medications (moeq) until hospital discharge.

NRS pain scores measured at arrival to PACU, PACU discharge, and every 4 hours until time of hospital discharge following surgery will be analyzed using repeated measures ANOVA with pairwise treatment comparisons performed using linear contrasts.

Postoperative complications will be compared across groups using the chi-square test and hospital length of stay (number of postoperative days) will be compared across treatment groups using the Kruskal-Wallis test with supplemental pairwise comparisons performed using the rank sum test. Similar analyses will be performed for additional endpoints collected at the 12-16 week follow-up visit including NRS pain scores and SF-12 scales.

Our primary analysis will be performed based on the intention to treat. All calculated p-values will be two sided. For the overall analyses comparing across all 3 treatment groups simultaneously p-values less than 0.05 will be considered statistically significant. For supplemental pairwise treatment group comparisons p-values less than 0.017 (Bonferroni adjusted) will be considered statistically significant. The statistical analysis will be performed using SAS version 9.4 (SAS Institute Inc., Cary, North Carolina, United States).

Handling of Missing Data

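### The 12-16 week SF-12 and rest-pain comparisons in section 7.2 ignore baselines already collected: valid, but some precision may be lost; adjust only with a baseline fixed before allocation is retrieved

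*Combined protocol and SAP*

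**What the plan says.** Section 7.2 (Statistical Methods) gives baseline data two uses: summary, and a between-group test ("Baseline characteristics will be compared across groups using analysis of variance, or the Kruskal-Wallis test for continuous variables"). It names no covariate, ANCOVA or change-from-baseline analysis for any outcome.

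The 12-16 week outcomes get one sentence: "Similar analyses will be performed for additional endpoints collected at the 12-16 week follow-up visit including NRS pain scores and SF-12 scales". The sentence before it plans a chi-square test for complications, and a Kruskal-Wallis test with pairwise rank-sum tests for length of stay. The natural reading for NRS and SF-12 is therefore the rank tests, which take no covariate.

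Both outcomes have a matching preoperative value. Section 3.3 says of SF-12: "Collected preoperatively and at the 12-16 week postoperative visit or telephone call". Section 6.1 says of rest pain: "Following informed consent and randomization, study staff will record baseline patient demographics (including baseline NRS values for pain at rest", with the values taken "from the electronic medical record and/or during the patient interview". Movement pain is asked at 12-16 weeks, but no baseline for it is listed.

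Section 5.7 declares the trial unblinded. Section 5.3 has a research-unit member retrieve the allocation once a patient is enrolled. Section 4.3 allows patients to be met for enrolment on the morning of surgery.

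**The concern.** SF-12 is measured twice with the same instrument, and the first measurement plays no part in estimating the treatment effect. The same holds for rest NRS. If the baseline predicts the 12-16 week value, adjusting for it removes part of the between-patient variation and makes the comparison sharper without adding patients.

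The obvious repair carries its own risk. A baseline covariate is safe when the assigned arm cannot have influenced it. Section 6.1 has staff record baseline NRS after randomization in an unblinded trial, and section 6.2 allows sedation before the interscalene block in two of the three arms ("with intravenous midazolam (1-4 mg) and fentanyl (50-200 mcg) for alleviation of anxiety and pain"). A value obtained after the allocation is known could differ by arm, and adjusting for it could then introduce bias that the present plan does not have.

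**Working it through.** **Inputs from section 7.1.** 39 per group; pairwise two-sided alpha 0.017; OBAS difference 3 with SD 3; NRS difference 0.75 SD, about 2.25 units, so an implied SD of 2.25/0.75 = 3.

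**Assumptions.** The baseline-outcome correlation r is not documented, so 0.1 to 0.5 is shown. No target difference is given for any 12-16 week outcome; the protocol's 0.75 SD for NRS is borrowed as an illustration. Data are taken as normal. The number followed to 12-16 weeks may be below 39 per group.

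**The plan's own figures.** A two-sample noncentral t calculation with n = 39 and alpha 0.017 gives 97.4% power for OBAS (d = 3/3 = 1; stated as above 90%) and 80.6% for NRS (d = 0.75; stated as 80%). Both reproduce, and neither relies on baseline adjustment.

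**Parametric guide to the gain.** Adjustment multiplies the variance of the treatment contrast by 1 − r², so the effective d is 0.75/√(1 − r²).

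| r | 1 − r² | Standard error falls by | t-based power |
|---|---|---|---|
| 0 | 1.00 | 0 | 80.6% |
| 0.1 | 0.99 | 0.5% | 81.0% |
| 0.2 | 0.96 | 2.0% | 82.4% |
| 0.3 | 0.91 | 4.6% | 84.6% |
| 0.5 | 0.75 | 13.4% | 91.4% |

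In patients, r = 0.3 is worth 39/0.91 = 42.9 per group and r = 0.5 is worth 39/0.75 = 52.

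**The tests that matter here.** Because section 7.2 plans rank tests, the relevant comparison is rank-sum against ANCOVA on ranks (Quade's method). Simulation with 20,000 runs, 39 per group and a 0.75 SD shift gives:

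| r | Rank-sum | Rank ANCOVA |
|---|---|---|
| 0.1 | about 78% | 78.5% |
| 0.2 | about 78% | 79.4% |
| 0.3 | about 78% | 81.8% |
| 0.5 | about 78% | 88.8% |

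Rank ANCOVA rejects a true null in 1.7% to 1.8% of runs against a nominal 1.7%. The t-based detectable difference at 80% power (0.745 SD unadjusted, less with adjustment) should not be carried over to these tests: at those differences the rank tests reach only about 76% to 78%.

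**Timing.** With equal SDs, a baseline shifted in one arm biases the ANCOVA estimate by −r × shift. For an illustrative 0.5-point NRS shift, that is 0.5 × 0.1 = 0.05, 0.5 × 0.2 = 0.10, 0.5 × 0.3 = 0.15 and 0.5 × 0.5 = 0.25 points. For shifts of 0.25 and 0.5 SD, simulated type I error of parametric ANCOVA at nominal 0.017 is 0.024 and 0.043 at r = 0.3, and 0.038 and 0.116 at r = 0.5. With no shift it stays at 0.017 to 0.018.

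**Missing baselines.** With 20% missing at random and replaced by the all-arm mean, parametric ANCOVA gives mean estimates of 0.748 to 0.752 SD (true value 0.75) and null rejection of 0.016 to 0.019.

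**The case against.** The strongest reply is that nothing is wrong. Unadjusted randomized comparisons are valid, the power statement does not depend on adjustment, the primary endpoint is untouched, and every figure for the gain rests on an assumed r. All of that stands, and it is why the priority is low. That SF-12 should benefit most is an inference from using the same instrument twice, not something the documents report.

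A second reply is that adjustment replaces an analysis needing no operational discipline with one that depends on the order of preoperative steps. This also stands. It is the reason to make the timing change and the adjustment together or not at all.

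Two stronger readings are tempting.

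- A reader might infer that the baseline NRS is a post-allocation value and so unusable. Section 6.1 says when staff record it, and a value taken from the medical record may be older. Section 3.1 has baseline values established before perioperative data collection, and the schedule in section 6.3 puts pain scores and SF-12 in a preoperative column separate from the day of surgery. No text places SF-12 after randomization. The order is unstated rather than wrong.
- A reader might infer that the in-hospital pain analyses are also deficient, because they too lack a baseline term: the across-group comparison ("Similar analyses will be performed for secondary endpoints of pain and total additional opioid medications (moeq) until hospital discharge") and the repeated-measures model that "will be analyzed using repeated measures ANOVA with pairwise treatment comparisons performed using linear contrasts". The documents give no ground for expecting preoperative rest pain to predict pain in the first hours after surgery, and at low r the gain may be negligible.

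**Conclusion.** The point holds as an efficiency improvement on two secondary outcomes, SF-12 scales and rest NRS at 12-16 weeks. It does not show bias, invalid tests or a shortfall in stated power.

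Under the borrowed 0.75 SD, normal data and 39 per group, the gain over rank-sum is about 1 point of power or less at r of 0.1 to 0.2, about 4 points at r = 0.3 and about 11 points at r = 0.5. Which of these applies cannot be settled from the documents. The unstated timing does no harm to the planned unadjusted comparisons; it matters only once a baseline becomes a covariate.

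**What to change.** 1. In sections 5.3 and 6.1, state that baseline rest NRS and SF-12 are obtained after consent and before the allocation is retrieved, and that an NRS taken from the record must be an entry made before that point.
2. In section 7.2, prespecify rank-based ANCOVA (ranks of the outcome adjusted for ranks of the baseline) as the governing analysis for 12-16 week SF-12 scales and rest NRS, each on its own baseline, with the significance thresholds already stated. Keep the planned unadjusted rank tests as a sensitivity analysis.
3. Keep patients whose baseline is missing by substituting the mean of observed baselines over all arms.

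Leave OBAS, opioid use, movement NRS and the in-hospital pain analyses as planned. A baseline term in the in-hospital repeated-measures model is optional.

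The cost is wording in three sections and a fixed order of preoperative steps, including when consent is given on the morning of surgery; if no earlier NRS entry exists, staff ask for one rest score then. No new instrument and no more patients are needed. Items 1 and 2 should be adopted together: adjusting without fixing the timing could leave the trial worse off than the present plan.

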Diagnosis and Main Inclusion Criteria	Patients presenting for unilateral primary total shoulder arthroplasty (includes anatomic and reverse total shoulder arthroplasty), who are able to provide to consent, older than 18 years of age, and have American Society of Anesthesiologists (ASA) physiological status I-III
Study Product, Dose, Route, Regimen	Ropivacaine weight base dose mixed with epinephrine, ketorolac, and normal saline 0.9% injected once in the periarticular structures of the shoulder joint by the surgeon
Duration of Administration	One time injection
Reference therapy	Interscalene brachial plexus block utilizing bupivacaine hydrochloride
Statistical Methodology	Randomization of each patient to a study arm will occur in a 1:1:1 allocation utilizing randomization schedule which will be created by the Division of Biomedical Statistics and Informatics. Subgroup analysis will be performed evaluating reverse total shoulder arthroplasty vs anatomic total shoulder arthroplasty, and patients who received allocated treatment per planned protocol

Introduction

This document is a clinical research protocol. The described study will be conducted in compliance with the protocol, Good Clinical Practices standards and associated Federal regulations, and all applicable institutional research requirements.

This document is a protocol for a human research study. This study will be carried out in accordance with the applicable United States government regulations and Mayo Clinic research policies and procedures.

Use of study medications within this study is not intended to be reported to the FDA in support of a new indication for use or to support any other significant change in the labeling for the drug. Additionally, use of study medications within this study is not intended to support a significant change in the advertising for the product.

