3.1 General Design

Single-center, unblinded, randomized control trial with three intervention arms assessing acute pain management. These three arms include: 1) single shot interscalene blockade (SISB group); 2) continuous interscalene nerve block (CISB group); 3) local infiltration analgesia (LIA group) into the periarticular soft tissues at the time of shoulder replacement.

The study will be registered with www.ClinicalTrials.gov

After approval by Mayo Clinic IRB, we will work closely with the department of orthopedics at Mayo Clinic Hospital, Methodist Campus to enroll patients into the study. Potential subjects will consist of patients who present for elective primary TSA meeting the inclusion and exclusion criteria (sections 4.1 and 4.2). Subjects will be approached by study staff for recruitment in person and informed consent will be obtained. Subjects unable to give consent themselves will not be approached for participation. No remuneration will be provided. All efforts will be made to enroll participants regardless of ethnic heritage. No passive recruitment methods (newspapers, advertisements, or flyers) will be used.

One hundred and twenty-nine patients are required for this clinical trial. After baseline values are established, data will prospectively be collected during the peri-operative period up to 16 weeks post-operatively (patient will have follow-up via office visit or telephone call) for the purpose of this study. Data will continue to be collected up to 1.5 years post-operatively, particularly the ASES score, and resulting data will plan to be used in a follow-up study. Data will be collected utilizing the institution's electronic medical record system, and be transferred to an electronic research database (REDCap).

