7.1 Sample Size Determination

The sample-size for this study was determined in order to provide statistical power of >90% to detect a difference of 3 units for the primary endpoint (OBAS on POD1). Based on a previous study, we hypothesize that the standard deviation of OBAS will be approximately 3 units.⁴⁴ Under this assumption, an effective sample-size of N=39 per group will provide statistical power of >90% to detect a difference between groups of 3 units using a two-sided, alpha=0.017 (multiple-comparison adjusted for 3 groups), non-parametric test. In addition, for the key secondary endpoint of pain (NRS), this sample-size will provide statistical power of 80% to detect a difference of 0.75 standard deviations (approximately 2.25 units on the NRS). In order to accommodate attrition of approximately 10% (due to canceled surgery, failed block, etc.) we propose a total sample-size of N=129 (43 patients per group).

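### With exactly three arms, the Bonferroni 0.017 threshold for every pair is valid but stricter than needed; a written gate with 0.05, or Holm, gains power at about the same 5% error within each endpoint

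*Combined protocol and SAP*

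**What the plan says.** Section 3.1 describes a three-arm trial: "Single-center, unblinded, randomized control trial with three intervention arms assessing acute pain management". Section 7.2 starts with an overall comparison; the primary endpoint "will be compared across groups using ANOVA (or the Kruskal-Wallis test"). The overall level is 0.05: "For the overall analyses comparing across all 3 treatment groups simultaneously p-values less than 0.05 will be considered statistically significant". Pairs are then judged at a stricter level: "For supplemental pairwise treatment group comparisons p-values less than 0.017 (Bonferroni adjusted) will be considered statistically significant".

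The 0.017 threshold appears twice in Section 7.2. The first statement is attached to OBAS and carries over to pain and total opioid use; the second is a general rule for all endpoints. All tests are two-sided ("All calculated p-values will be two sided"). Section 7.1 used the same level for the sample size: "two-sided, alpha=0.017 (multiple-comparison adjusted for 3 groups), non-parametric test".

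The plan does not say whether a pairwise test may be declared only after a significant overall test. It also gives no reason for combining an overall test with a full Bonferroni division.

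**The concern.** Bonferroni at 0.05/3 protects the three pairwise tests without help from the overall test. The plan runs the overall test as well, but gives it no role in error control. With three arms the overall test could do nearly all of that work, and each pair could then be tested at 0.05.

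What is at stake is power. It matters most for the key secondary endpoint NRS, which Section 7.1 powers at 80%. The same threshold applies to total opioid use, length of stay and the 12-16 week outcomes, for which Section 7.1 states no power. The study hypothesis is that CISB beats both other arms, so the chance of showing both advantages is of interest alongside the chance for a single pair.

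**Working it through.** **Inputs.** From Section 7.1: OBAS difference 3 and SD 3 (1.0 SD); NRS difference 0.75 SD; 39 per group effective; two-sided alpha 0.017; stated power >90% and 80%. From Section 7.2: overall alpha 0.05 and pairwise alpha 0.017.

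**Step 1: the plan's own figures.** Power ≈ Φ(d·√(n/2) − z), with z = 2.387 for two-sided 0.017.
- OBAS: 1.0 × √19.5 = 4.416; 4.416 − 2.387 = 2.029; power 97.9%. With n multiplied by 0.955 (rank-test efficiency under normality) it is 97.3%. Both agree with >90%.
- NRS: 0.75 × 4.416 = 3.312; 3.312 − 2.387 = 0.925; power 82.3%. With rank efficiency it is 80.2%, which matches 80%.

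The stated power is therefore met, per pair, at 0.017.

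**Step 2: why the gated rule is valid.** Call the arms A, B and C. If any two of A=B, A=C and B=C hold, all three hold. The closed family is then just the three pairs and the overall null.
- All arms equal: a false claim needs a significant overall test, so its chance is at most 5%.
- Exactly one pair equal: only one true pairwise null exists, and it is tested at 5%.
- No pair equal: no false pairwise claim is possible.

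Holm needs no gate. The smallest p-value is compared with 0.05/3, the next with 0.05/2 and the largest with 0.05. It rejects everything that Bonferroni at 0.05/3 rejects.

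**Step 3: simulated family-wise error.** Normal data, equal SD, 39 per arm, 100,000 trials per setting. Ranges cover ANOVA with t tests and Kruskal-Wallis with rank-sum tests.

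| Rule | All three equal | One arm different |
|---|---|---|
| Pairs at 0.017, no gate | 4.4% | 1.6-1.7% |
| Pairs at 0.017, gated | 3.9-4.0% | 1.6-1.7% |
| Pairs at 0.05, gated (closed test) | 4.9% | 4.6-5.0% |
| Pairs at 0.05, no gate | 12.1-12.2% | 4.9-5.0% |

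**Step 4: simulated power, rank tests.** Holm figures come from a smaller simulation (20,000 trials per setting) and were obtained for the 0.75 SD case.

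| CISB better than both others by | Claim | Bonferroni 0.017 | Holm | Closed test |
|---|---|---|---|---|
| 0.75 SD (NRS) | one CISB pair | 78.0% | about 81% | 86.7% |
| 0.75 SD (NRS) | both CISB pairs | 66.2% | about 72% | 81.5% |
| 1.0 SD (OBAS) | one CISB pair | 96.6% | – | 98.7% |
| 1.0 SD (OBAS) | both CISB pairs | 94.0% | – | 98.0% |
| 0.5 SD | one CISB pair | 38.6% | – | 48.5% |

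For NRS the closed test gains 86.7 − 78.0 = 8.7 points per pair and 81.5 − 66.2 = 15.3 points for both. For OBAS it gains 98.7 − 96.6 = 2.1 and 98.0 − 94.0 = 4.0 points.

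**Step 5: a less favourable pattern.** If the third arm lies midway, the extreme pair gains less: NRS 77.8% to 81.1% (3.3 points), OBAS 96.7% to 97.4% (0.7 points).

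**The case against.** **The plan has no defect here.** The 0.017 rule is pre-specified, stated consistently and valid, and the sample size already pays for it. This stands. A reader might infer that the trial falls short of its promised power, particularly since both NRS comparisons together reach only about 66%. The documents do not support that: Section 7.1 gives 80% for a difference between groups, which is a per-pair figure, and Step 1 reproduces it.

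**The type I error is not too high.** A reader might note that 3 × 0.017 = 0.051 and infer that the 5% limit is broken. The 0.017 is 0.05/3 = 0.0167 rounded, and the simulated error with all arms equal is 4.4%.

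**The stricter threshold does buy something.** A reader might infer that it brings no gain in error control. When one arm differs, Bonferroni rejects the truly equal pair about 1.6% of the time, against about 5% for the closed test. Neither method controls error across the many endpoints, so a stricter pairwise threshold is a defensible choice.

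**The gated rule is not uniformly better.** With a midway arm at 0.75 SD, about 0.6% of trials (77.81% − 77.20%) have p<0.017 for the extreme pair but a non-significant overall test, and the gate forfeits that claim. Holm avoids this.

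**Control at 5% depends on similar spread.** Assuming one of two equal-mean arms has twice the SD and the third arm is shifted by 1 SD, the equal-mean pair was rejected in 6.0% of simulated trials under the closed test, against 2.0% at 0.017.

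**Bonferroni has simple matching simultaneous confidence intervals.** The closed test does not. That is a legitimate reason to keep Bonferroni.

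These points limit the concern to efficiency. They do not remove the gain on NRS.

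**Conclusion.** Section 7.2 is valid but conservative. With exactly three arms, the closed test gains about 9 points of power per CISB pair and about 15 points for both pairs at the NRS planning effect, with family-wise error still about 5% within each endpoint and no added patients. Holm gains about 3 and 6 points (78% to 81%; 66% to 72%). For OBAS at the planned 1.0 SD the gain is about 2 points per pair and 4 for both, from power that already exceeds the target. It would matter more if the true effect were smaller.

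The figures assume 39 evaluable patients per arm, normal data and equal SD. The larger ones also assume that CISB is better than both other arms by the same amount; with a midway third arm the extreme pair gains about 3 points on NRS. This is an inexpensive improvement that the sponsor may reasonably adopt. It does not show a fault in error control or in the sample size.

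**What to change.** Before the data are analysed, replace **both** 0.017 statements in Section 7.2: the one attached to OBAS, which also governs pain and opioid use, and the general rule. Changing only one would leave two conflicting thresholds. Suggested wording:

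> A pairwise comparison is significant only if the overall three-arm test for that endpoint and the pairwise test both have p<0.05 (closed testing for three groups).

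If no gate is wanted, specify Holm-adjusted p-values for the three pairs instead. For the repeated-measures NRS analysis, name as the gate the overall treatment test that matches the contrasts being made. Report adjusted p-values.

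The gate must be written in: changing 0.017 to 0.05 without it would raise family-wise error to about 12% when all arms are equal. Section 7.1 can stay as it is, because a sample size calculated at 0.017 is a conservative basis.

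The cost is two edited statements plus the NRS gate. The price in inference is the loss of simple matching simultaneous intervals, rejection of a truly equal pair up to about 5% rather than about 1.6% of the time when the third arm differs, and error slightly above 5% if spreads are unequal. Error across endpoints remains uncontrolled, as it is now.
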